5.4. Death

A summary of the number of deaths since first administration of study agent up to + 30 days after last ibrutinib or up to 100 days after last dose of nivolumab whichever is last, will be provided, along with the primary cause of death. A death is a study drug-related death if the primary cause is a drug-related adverse event.

5.5. Clinical Laboratory Tests

Laboratory data for hematology and serum chemistry tests, up to the later of the End of Treatment visit or up to + 30 days after last ibrutinib or up to 100 days after last dose of nivolumab whichever is last, will be reported in SI units. Applicable laboratory results will be graded according to NCI-CTCAE Version 4.03. Toxicity grading for creatinine increase is based on the NCI-CTCAE v4.03 criteria but limited only to the part based on the ULN, the other part that is based on change from baseline is not used for toxicity grading. Toxicity grading for all other lab parameters are based on the NCI-CTCAE v4.03 criteria as is.

The following laboratory tests will be analyzed:

- Hematology: hemoglobin, white blood cell count (WBC), absolute neutrophil count (ANC), absolute lymphocyte count (ALC), and platelet count
- Chemistry: sodium, potassium, magnesium, creatinine, creatinine clearance (CrCl), AST, ALT, alkaline phosphatase, LDH, total bilirubin, albumin, amylase and lipase.
- Beta2-microglobulin, serum immunoglobulin levels (IgG, IgM, IgA): only for FL and CLL/SLL disease cohorts.
- Coagulation panel: PT APTT and INR
- Thyroid function: T3 free T4 and TSH

Descriptive statistics (mean, standard deviation, median, and range) will be calculated for the raw data and for change from baseline at each time point of assessment, as well as for change from baseline to the last value. Worst toxicity grade will be summarized for all hematology and chemistry parameters except for LDH, which will be summarized by abnormal/normal using normal ranges. Change from baseline to the worst grade during the treatment will be provided as shift tables for selected parameters.

Lymphocytosis is defined as ALC increasing $\geq 50\%$ from baseline and achieving level $\geq 5 \times 10^9$ /L. Descriptive statistics will be provided for time to first lymphocytosis, i.e., time from first dose to date of first lymphocytosis. Similar to duration of response, Kaplan-Meier method will be used to estimate duration of first lymphocytosis as the time from first lymphocytosis to the earliest date of its resolution (i.e., when ALC decreased to the baseline level or lower or achieving level of $< 5 \times 10^9$ /L) or date of censoring (i.e., date of last non-missing ALC).

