| Serum chemistry | Sodium, potassium, magnesium, creatinine, total bilirubin, glucose (only at Screening), albumin, AST, ALT, alkaline phosphatase, LDH, amylase and lipase. Not repeated on CID1 or CID-7 if obtained within 48 hours. Perform within 48 hrs prior to the start of each cycle; results must be reviewed prior to each nivolumab infusion. | X | X | X | X | X (only at first FU < 100 days after last dose of nivolumab) |
| Coagulation panel | PT, APTT, INR Perform within 48 hrs. prior to the start of applicable cycle; results must be reviewed prior to the nivolumab infusion. | | X | as clinically indicated | X | |
| Thyroid function | T3, free T4, TSH Perform within 48 hrs. prior to the start of applicable cycle; results must be reviewed prior to the nivolumab infusion. | X | Q4cycles (starting cycle 5) | | | |
| $\beta 2$ microglobulin and serum Ig | Only for FL and CLL/SLL Perform within 48 hrs. prior to the start of applicable cycle; results must be reviewed prior to the nivolumab infusion. | | X | Q8cycles (starting cycle 9) during the first year, thereafter Q16cycles | | |

| | Notes | Screening Period | Treatment Period (14 day cycles) | | Follow-up Period ^a |
|---|---|---|---|---|-------------------------------|
| | | up to 28 days before start of any study treatment | BASELINE ASSESSMENT CID1 (without run-in phase) CID-7 (with run-in phase) | Day 1, subsequent cycles | EOT |

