2.2. Visit Windows

Visit window will be based on phases and cycles:

(For the purposes of this study, ‘study drug’ or ‘study therapy’ or “study treatment” refers to both ibrutinib and/or nivolumab).

Screening: Up to 28 days before the start of any study treatment.

Treatment: Between the date of first administration of study therapy and the date of the last dose of study drug. The treatment stage will be subdivided by cycles. Each cycle is 14 days, starting from the first dose of study drug. The end date of the last cycle is the date of the last dose of study drug received during the study.

End of treatment: within 30 days after the last dose of ibrutinib or 100 days after the last nivolumab. The assessments performed during the ‘End of treatment visit’ will be included in this End of treatment phase.

Follow-up: After the end of treatment till the last assessment for the last subject in the study (e.g. the last follow-up visit or death).

Baseline assessment is defined as the last non-missing results on or before the first dose of study therapy.

1. Cycle-based analysis may be performed for safety parameters during the treatment up to date of last dose of ibrutinib + 30 days, and last dose of nivolumab +100 days. For the analysis of laboratory measurement by cycle, the mean values within each cycle will be used. For the analysis of laboratory grade by cycle, the worst grade within each cycle will be used.

Assessments will be presented chronologically by cycle day or study day, which are defined as the follows:

Day 1 = date of first dose of study drug / Cycle 1 day -7 (subjects with run-in)

Study Day (if on or after date of first dose) = assessment date – date of first dose +1

Study Day (if before date of first dose) = assessment date – date of first dose

Cycle Day = assessment date – date of first dose for the cycle +1

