5.1. Adverse Events

The verbatim terms used in the CRF by investigators to identify adverse events will be coded using the current Medical Dictionary for Regulatory Activities (MedDRA). The severity of adverse events is assessed in NCI common toxicity criteria for adverse events (CTCAE) Version 4.03.

Treatment-emergent adverse events are 1) adverse events that occur after the first dose of study treatment, and up to + 30 days after last ibrutinib or up to 100 days after last dose of nivolumab whichever is last, or the start date of a subsequent systemic anticancer therapy, whichever is earlier (including both dates), 2) any adverse event that is considered study treatment - related (at least relationship to one drug of combination will be considered related) (i.e., possibly, probably, or very likely related to study drug) regardless of the start date of the event, 3) any adverse event that is present at baseline but worsens in severity and is subsequently considered drug-related by the investigator.

Treatment-emergent adverse events will be summarized by system organ class (SOC) and preferred term (PT), by severity, by relationship to study treatment, and by action taken. For each adverse event, the percentage of subjects who experience at least 1 occurrence of the given event will be summarized. Tables will be sorted by frequency in incidence (from the highest to lowest incidence). The same summary will be provided for drug-related adverse events, serious adverse events, and drug-related serious adverse events, immune-related events as well as adverse events leading to treatment discontinuation, and death.

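### SAP 5.5 does not end the laboratory window at the start of subsequent anticancer therapy, as SAP 5.1 does for time-based adverse events, so values taken on next-line treatment can enter the worst-grade and last-value summaries

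*SAP*

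**What the plan says.** **Adverse events (SAP 5.1).** The time-based window for treatment-emergent events runs to the later of 30 days after ibrutinib and 100 days after nivolumab, "or the start date of a subsequent systemic anticancer therapy, whichever is earlier (including both dates". Events judged related to study treatment are kept "regardless of the start date of the event".

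**Laboratory data (SAP 5.5).** Hematology and chemistry up to the later of the End-of-Treatment visit or 30 days after ibrutinib or "up to 100 days after last dose of nivolumab whichever is last, will be reported in SI units". Subsequent therapy is not mentioned. The outputs include:

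- Worst grade: "Worst toxicity grade will be summarized for all hematology and chemistry parameters except for LDH".
- Change from baseline at each time point and to the last value, with no further limit on period.
- Shift tables, worded more narrowly: "Change from baseline to the worst grade during the treatment will be provided as shift tables for selected parameters".

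**Treatment period (SAP 2.2).** The treatment phase is "Between the date of first administration of study therapy and the date of the last dose of study drug". The rule for cycle-based safety analysis in the same section lets treatment extend to 30 days after ibrutinib and 100 days after nivolumab, also without a cut at subsequent therapy.

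**Sampling (protocol Table 1).** If new anticancer therapy is needed before the End-of-Treatment visit, that visit is brought forward to just before it. The only chemistry scheduled afterwards is marked "only at first FU < 100 days after last dose of nivolumab". The follow-up cell for hematology is empty.

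**The concern.** Two safety outputs for the same subjects treat next-line therapy differently, and the SAP gives no reason. Elsewhere it does take account of that date: response counts only at or before subsequent therapy (4.2.1), symptom resolution is assessed before it (4.3.4), and imputed adverse event start dates can be capped at it (2.6). Its absence from 5.5 therefore looks like an omission.

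A date rule matters more for laboratory data than for adverse events. An adverse event carries a relatedness judgement, so a late drug effect can be kept and an unrelated one dropped. A laboratory value has no such rating, and the date is the only filter. The follow-up panel contains creatinine, AST, ALT and bilirubin, and rises in these appear in the hepatic and renal immune-related term lists in SAP 5.3. An unrelated rise that follows salvage treatment could be outside the treatment-emergent tables yet set the subject's worst grade or last value.

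**Working it through.** There is no stated figure to reproduce. The check compares the two windows and then asks which samples can fall in the gap.

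**Step 1: size of the gap.** Put the last dose of both drugs on day 0 and let next-line therapy start on day *s* (assumed). The time-based adverse event window ends on day min(100, *s*). The laboratory window ends on day 100. The gap is 100 − min(100, *s*).

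| *s* (days) | Adverse event window ends | Laboratory window ends | Gap (days) |
|---|---|---|---|
| 7 | 7 | 100 | 93 |
| 14 | 14 | 100 | 86 |
| 30 | 30 | 100 | 70 |
| 60 | 60 | 100 | 40 |
| 90 | 90 | 100 | 10 |
| 100 or later | 100 | 100 | 0 |

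Protocol 9.5 permits subsequent therapy once progression is established and sets no waiting period, so small values of *s* are possible.

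**Step 2: which scheduled samples can fall in the gap.**

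- *End-of-Treatment panel:* none. Under Table 1 it comes before new therapy.
- *Chemistry after End of Treatment:* at most one panel, at the first follow-up. Table 1 places this visit approximately 100 days after nivolumab and gives follow-up visits a window of ±7 days. If that window applies around day 100, the draw falls between day 100 − 7 = 93 and day 100 + 7 = 107. Draws on days 93 to 100 are inside the SAP 5.5 limit; draws on days 101 to 107 are outside it, unless ibrutinib stopped late enough for its own 30-day limit to govern. The serum chemistry cell, as printed, puts the draw before day 100.
- *Hematology after End of Treatment:* none scheduled. Protocol 10.6 allows extra tests when clinically indicated, so hematology can enter only that way.

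**Step 3: which summaries are exposed.**

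- *Worst grade:* exposed, because it has no limit narrower than the 5.5 window.
- *Change to last value:* exposed. A usable value exists at End of Treatment, but an in-window follow-up panel would replace it.
- *Shift tables:* not clearly exposed. Read with the treatment phase in SAP 2.2 they stop at the last dose; read with the cycle-based rule in the same section they run to the 30- and 100-day limits.

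**Step 4: illustrative effect on worst grade.** The documents give neither rate needed. Let *f* be the share of a 35-subject cohort that starts next-line therapy before an in-window follow-up panel, and *q* the share of those with a new high grade on it. Extra subjects = 35 × *f* × *q*.

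- Low: 35 × 0.10 × 0.05 = 0.175, about 0.2 subjects (0.5 percentage points).
- High: 35 × 0.50 × 0.20 = 3.5 subjects (10 percentage points).

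Both ranges are assumptions. They show scale only.

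**The case against.** The strongest defense is that the uncut window follows the planned safety follow-up. Protocol 3.1 follows subjects to the later of 30 days after ibrutinib and 100 days after nivolumab and includes laboratory assessments at the first follow-up; SAP 5.4 uses the same uncut period for deaths. Late immune-related changes are a reason to look that far. This stands as a reason to collect and show the values. It does not explain why a value taken on another regimen should replace the End-of-Treatment value as the last value, or set the worst grade, without being marked.

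A second defense is that the 5.1 cut does not transfer cleanly. Since 5.1 keeps related events at any date, adverse event tables can themselves contain events after next-line therapy, and sites record only clinically relevant laboratory changes as adverse events. Full agreement between the tables should therefore not be expected even after the fix. That is correct and limits what the fix can claim. Follow-up chemistry can also be seen separately in the by-time-point summaries, which helps but leaves worst grade and last value as they are.

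Two stronger readings are tempting and are not supported:

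- *That next-line toxicity is reported as study-drug toxicity.* SAP 5.5 assigns no cause to laboratory values. Its summaries are all-cause, and the issue is which samples they may include.
- *That most of an aggressive-lymphoma cohort would have an affected last value.* SAP 1.2 expects a median of about 2 months on therapy in DLBCL. A reader might assume from this that 50 to 80% start new therapy before the follow-up draw, or 35 × 0.5 = 17.5 to 35 × 0.8 = 28 subjects. Time on therapy does not say when the next treatment starts, and the calculation ignores subjects who die, miss the visit or are sampled after the limit.

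**Conclusion.** The mismatch is real: 5.1 cuts its time-based window at subsequent systemic anticancer therapy, 5.5 does not, and no other section of the SAP supplies the cut. Post-switch values can enter the worst-grade and last-value summaries; whether they do depends on when next-line therapy starts and when the sample is drawn. The scheduled exposure is bounded at one chemistry panel per subject and no hematology panel. The number of subjects affected is unknown, and the 0.2 to 3.5 per 35 in the working rests wholly on assumed rates.

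This is a minor point about descriptive safety tables in an uncontrolled study. Overall response rate and the dose-limiting toxicity decisions do not depend on it. It is worth correcting because the correction is cheap and applies a rule the SAP already uses.

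**What to change.** In SAP 5.5:

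1. For worst grade and change to last value, end the window at the earlier of the date now stated and the start of subsequent systemic anticancer therapy.
2. List results after that date separately, by subject, with the start date of the new therapy, so that late drug effects stay visible.
3. Define the period meant by treatment in the shift tables: either first to last dose, or to the 30- and 100-day limits with the same cut.

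If the sponsor prefers the wider window, the alternative is to state the reason and show both summaries with and without the later samples.

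The cost is a few sentences and one listing. Start dates of subsequent therapy are already collected under protocol 9.5. The downside is that a late drug effect first seen after new therapy would appear only in the listing, so the listing should be reviewed together with the tables.

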5.5.1. Creatinine Clearance

Creatinine clearance (CrCl) is calculated using the Cockcroft-Gault formula:

$$\text{CrCl}_{\text{(est)}} = \frac{(140 - \text{age}[\text{yr}])(\text{lean body wt}[\text{kg}])}{(72)(\text{serum creatinine}[\text{mg/dL}])} \times 0.85 \text{ (if female)}$$

for males, the factor is 1 instead of 0.85

5.6. Other Safety Parameters

Change in ECOG scores from baseline to the worst score during the treatment will be provided as shift tables.

Subjects with more than 10% weight loss from baseline will be summarized.

- Change in ECG (QTcF only) from baseline to the worst score during the treatment will be provided as shift tables
- Listing of transfusion dependency by subject
- Listing of requirement of gCSF by subject

6. Pharmacokinetics

The plasma concentration data for ibrutinib and, if possible and judged relevant, PCI-45227 and other metabolites, if possible, will be summarized at each time point using descriptive statistics.

Population pharmacokinetic analysis of plasma concentration-time data will be performed using nonlinear mixed-effects modeling. Data may be combined with data from other studies to support a relevant structural population-based pharmacokinetic model. Available subject characteristics (demographics, laboratory variables, genotypes, etc.) will be tested as potential covariates affecting pharmacokinetic parameters. Details will be given in a population pharmacokinetic analysis plan and the results of the population pharmacokinetic analysis will be presented in a separate report.

Data will be listed for all subjects with available plasma concentrations. Subjects will be excluded from the pharmacokinetic analysis if their data do not allow for accurate assessment of the pharmacokinetic (e.g., incomplete administration of the study agent; concentration data not sufficient for pharmacokinetic parameter calculation due to missing pharmacokinetic draws at multiple visits; or early discontinuation from the study).

All concentrations below the lowest quantifiable concentration or missing data will be labeled as such in the concentration data presentation. Concentrations below the lowest quantifiable concentration will be treated as zero in the summary statistics. All subjects and samples excluded from the analysis will be clearly documented in the study report.

For each dosage, descriptive statistics, including arithmetic mean, standard deviation, coefficient of variation, geometric mean, median, minimum, and maximum will be calculated for the ibrutinib and PCI-45227 plasma concentrations at each sampling time and for all pharmacokinetic parameters of ibrutinib.

7. Biomarker

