| | | 4hr post dose | X ^e | X | | | | | | | |
| Cycle 25 | Day 1 | predose ^{a,b} | | X | X | X | X | | | | |
| Q8 cycles^o | Day 1 | predose ^{a,b} | | | | X | X | | | | |
| Q16 cycles^o | Day 1 | predose ^{a,b} | | X | X | | | | | | |
| At CR^o | | | | | X | | | | X ⁱ | | |
| At progression ^k | | | | X | X | | | X ^o | X ^o | | |
| EOT | | | X ^{f,o} | X ^f | | X ^{m,o} | X ^{m,o} | | | | |
| FU 1 (100 days after last dose of nivolumab) | | | | | | X ^o | X ^o | | | | |
| FU | | | | X (to be repeated Q6m starting at FU3) ^{n,o} | | | | | | | |

ADA=anti-drug antibodies; CR=complete response; EOT=End of Treatment; FNA=fine needle aspirate; FU=Followup; PD=pharmacodynamic; PK=pharmacokinetic

- a. Predose samples should be taken just prior to the administration (preferably within 30 minutes, however predose collection up to 4 hours before study drug administration would be acceptable). If the infusion is delayed and a predose sample was already collected, there is no need to collect an additional predose sample.
- b. When both study drugs are given, predose samples should be obtained prior to administration of any study drug.
- c. Required for Cohort B1 and B2 only.
- d. Cohorts A1, A2, B3, and B4 that did not have an ibrutinib run-in.
- e. If not done in Cycle 13, postdose samples for ibrutinib PK can be collected at a subsequent cycle.
- f. If possible, the EOT sample should be obtained within 48 hours after last intake of ibrutinib.
- g. Submission of tumor tissue from a biopsy performed during screening is mandatory (diagnostic block or slides), archival tissue is acceptable if fresh biopsy is not available.
- h. Extent of disease involvement in the bone marrow must be documented at screening based on the results of a bone marrow biopsy/aspirate performed within 90 days prior to enrollment or a bone marrow biopsy/aspirate performed during the screening period. If bone marrow biopsy/aspirate is performed during screening (after obtaining informed consent), submission of bone marrow aspirate is encouraged.
- i. If the bone marrow was involved by lymphoma at baseline, a bone marrow biopsy and/or aspirate will be required to confirm a CR. Submission of bone marrow aspirate to the central lab is required if clinically feasible.
- j. Subjects are required to undergo tumor and/or bone marrow biopsies from C13 onwards if clinically indicated. When tumor biopsy is performed, submission of tumor biopsy to the central lab is required if clinically feasible.

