4.2. Exclusion Criteria

Any potential subject who meets any of the following criteria will be excluded from participating in the study.

1. Major surgery within 4 weeks of the first dose of ibrutinib.
2. Diagnosed or treated for malignancy other than the indication under study except for:
 - Malignancy treated with curative intent and with no known active disease present for ≥ 3 years before the first dose of ibrutinib or nivolumab
 - Adequately treated non-melanoma skin cancer or lentigo maligna without evidence of disease
 - Adequately treated cervical carcinoma in situ without evidence of disease
3. History of stroke or intracranial hemorrhage within 6 months prior to the first dose of ibrutinib.
4. Requires anticoagulation with warfarin or equivalent vitamin K antagonists (eg, phenprocoumon).
5. Requires treatment with strong CYP3A inhibitors ([Attachment 8](#)).
6. Criterion modified per amendment 1
 - 6.1 Clinically significant cardiovascular disease such as uncontrolled or symptomatic arrhythmias, congestive heart failure, or myocardial infarction within 6 months of Screening, or any Class 3 (moderate) or Class 4 (severe) cardiac disease as defined by the New York Heart Association Functional Classification ([Attachment 3](#)), or congenital long QT syndrome, or QT interval corrected for heart rate, using Fridericia formula²¹ (QTcF) at Screening >470 ms.
7.
 - Subjects with a history of Human Immunodeficiency Virus (HIV)
 - Subjects who have active infection or are chronic carriers of Hepatitis B or Hepatitis C.
8. History of disallowed therapies:
 - Prior treatment/exposure with ibrutinib or other BTK inhibitor
 - Prior exposure to anti-PD1, anti-PDL1, anti-PD-L2, anti-CD137 or anti-cytotoxic T-lymphocyte associated antigen 4 (CTLA-4) antibody
 - Concurrent enrollment in another therapeutic investigational clinical study

9. Prior anti-tumor therapy including (all times measured prior to start of study therapy)
 - nitrosoureas within 6 weeks
 - chemotherapy within 3 weeks
 - therapeutic antibodies within 4 weeks
 - radio- or toxin-immunoconjugates within 10 weeks
 - radiation therapy within 3 weeks
 - investigational agents within 3 weeks
 - carmustine (BCNU) ≥ 1000 mg received as part of pre-transplant conditioning regimen
 - chest radiation ≤ 24 weeks prior to first dose of the study drug
10. Criterion revised per Amendment 4
 - 10.1 Known central nervous system (CNS) lymphoma.
11. Received an allogeneic hematopoietic SCT.

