12.5. Pharmacokinetic Analyses

The plasma concentration data for ibrutinib and, if possible and judged relevant, the metabolite PCI-45227, and serum concentrations of nivolumab at each timepoint will be summarized using descriptive statistics. Ibrutinib and nivolumab data will be listed by dose cohort for all subjects with available plasma/serum concentrations. Subjects will be excluded from the pharmacokinetic analysis if their data do not allow for accurate assessment of the pharmacokinetic (eg, incomplete administration of the study agent; concentration data not sufficient for pharmacokinetic parameter calculation due to missing pharmacokinetic draws at multiple visits; or early discontinuation from the study).

All concentrations below the lowest quantifiable concentration or missing data will be labeled as such in the concentration data presentation. Concentrations below the lowest quantifiable concentration will be treated as zero in the summary statistics and for the calculation of pharmacokinetic parameters. All subjects and samples excluded from the analysis will be clearly documented in the study report.

If non-compartmental analysis for ibrutinib/PCI-45227 is performed, results will be summarized using descriptive statistics.

Population pharmacokinetic analysis of ibrutinib plasma concentration-time data may be performed using NONMEM. Data may be combined with data from other studies to support a relevant structural population-based pharmacokinetic model. Available subject characteristics

(demographics, laboratory variables, genotypes, etc.) will be tested as potential covariates affecting pharmacokinetic parameters.

Model-derived exposure parameters may be subjected to further explore pharmacokinetic/pharmacodynamic correlation between exposure with relevant clinical or biomarker information.

Ibrutinib and nivolumab concentration data may be compared to observed concentration data and/or concentration estimates from the existing population PK models of ibrutinib/nivolumab, as appropriate.

If additional population PK analyses of ibrutinib and/or nivolumab are performed using data from this study, the results relevant for this study will be communicated, but an additional modeling report may be generated and will not be part of the study report for this study.

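### SAP section 6 sets concentrations below quantification to zero and also asks for a geometric mean at each sampling time, which one such value makes zero or undefined

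*SAP*

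**What the plan says.** Three statements in SAP section 6 (Pharmacokinetics) bear on this.

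- The rule for low values: "Concentrations below the lowest quantifiable concentration will be treated as zero in the summary statistics".
- The list of statistics, reported by dosage. After the arithmetic mean and standard deviation it continues: "coefficient of variation, geometric mean, median, minimum, and maximum will be calculated for the ibrutinib and PCI-45227 plasma concentrations at each sampling time".
- How such values are displayed: "All concentrations below the lowest quantifiable concentration or missing data will be labeled as such in the concentration data presentation". This concerns labelling in the data display. It does not remove the values from the summaries.

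The section gives no substitute value for the geometric mean, does not leave low values out of it, and does not say when it is not to be calculated. The separate population PK analysis plan is mentioned only for the modelling. No other SAP section returns to the subject.

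Protocol 12.5 has a similar rule: "Concentrations below the lowest quantifiable concentration will be treated as zero in the summary statistics and for the calculation of pharmacokinetic parameters". It asks only for descriptive statistics and does not name the geometric mean. The conflict therefore arises in the SAP.

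**The concern.** A geometric mean requires strictly positive values. The SAP writes zeros into the data and then asks for a statistic that cannot accommodate them. This is a stated rule that fails when followed, not a detail left open.

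Two things are at stake. If the rule is followed literally, a sampling time with dozens of measurable concentrations and one value below the limit reports a geometric mean of zero or a blank. If the software instead drops the zero silently, the geometric mean rests on fewer subjects than the arithmetic mean and median beside it, the written rule has not been followed, and the reader cannot tell which was done.

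**Working it through.** The plan states no figure on this point, so there is none to reproduce. The check is on the formula, the sampling schedule and the chance of a zero.

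**1. Effect of one zero.** The geometric mean is (x1 × x2 × … × xn)^(1/n), or equivalently exp of the mean of log(xi). With one xi = 0 the product is 0. In the log form, log(0) is minus infinity, which software returns as 0, missing or an error.

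- Seven made-up values 5, 10, 12, 20, 33, 40, 80: geometric mean 19.97, arithmetic mean 200/7 = 28.57, median 20.
- Add one value set to 0 (n = 8): geometric mean 0 or undefined, arithmetic mean 200/8 = 25.0, median (12 + 20)/2 = 16.0.
- If the zero is silently dropped from the geometric mean only, it stays at 19.97 on n = 7 beside a mean of 25.0 and a median of 16.0 on n = 8.

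At cohort size, 34 values of 10 and one zero give an arithmetic mean of 340/35 = 9.71 and a geometric mean of 0. From the 34 quantifiable values the geometric mean is 10.

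**2. Where zeros are expected by design.** Exclusion criterion 8 (Protocol 4.2) bars "Prior treatment/exposure with ibrutinib or other BTK inhibitor". Protocol Table 2 nevertheless schedules a predose ibrutinib sample before the first ibrutinib dose:

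- Day -7, which footnote c marks "Required for Cohort B1 and B2 only".
- Cycle 1 Day 1, which footnote d assigns to "Cohorts A1, A2, B3, and B4 that did not have an ibrutinib run-in".

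Essentially all of these samples should be below the limit. A geometric mean has nothing to summarise there, so little is lost.

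**3. Where a zero would cost something.** After the first predose sample, Table 2 schedules ibrutinib PK at 1, 2 and 4 hours after that dose, at Cycle 3 Day 1 predose, at Cycle 13 Day 1 predose and 1, 2 and 4 hours post-dose, and at end of treatment. Footnote f asks for the end-of-treatment sample within 48 hours of the last intake only where possible, so later samples can occur.

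**4. Chance of at least one zero at such a time.** With n samples and share q below the limit, taken as independent, the chance is 1 − (1 − q)^n. The documents do not give q; the values below are assumptions. The n of 35 is the planned Part B cohort size, and 9 is the upper cohort size in Part A.

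| q (assumed) | n = 9 | n = 35 |
|---|---|---|
| 1% | 9% | 30% |
| 2% | 17% | 51% |
| 5% | 37% | 83% |
| 10% | 61% | 97% |
| 20% | 87% | >99.9% |

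For example, at q = 2% and n = 35: 1 − 0.98^35 = 0.507.

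The number per table cell may differ from 35 in either direction. The SAP summarises by dosage, which may pool cohorts: if three Part B cohorts share a dose (assumption), n is 3 × 35 = 105 and the chances at 1%, 2% and 5% become 65%, 88% and 99.5%. Conversely, subjects who stop before Cycle 13 reduce n there, which lowers the chance.

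**The case against.** The strongest reply is that very little depends on this.

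- The SAP lists seven statistics and gives none priority. The arithmetic mean, standard deviation, median, minimum and maximum all remain computable with zeros, and so does the coefficient of variation unless every value is zero.
- The one near-certain case, the first predose sample, does no harm.
- For later samples the documents give neither an assay limit nor concentrations, so the frequency of zeros is unknown.

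All of this stands and limits the point. It does not remove the conflict, because nothing in either document says what to do when a zero occurs.

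A reader might infer more than the documents support:

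- **That the main summary of exposure, and with it the PK objective, is compromised.** Neither document makes the geometric mean the main summary. Protocol 12.5 allows a comparison with existing concentration data or model estimates without naming a geometric mean as its basis. Exposure metrics come from population modelling or optional non-compartmental analysis (Protocol 10.3.4 and 12.5). A geometric mean of Cmax or AUC is affected only if a subject's own value is zero. The SAP list covers ibrutinib and PCI-45227, not nivolumab.
- **That ibrutinib troughs will be below the limit.** The documents do not show this; it is possible, and the table above gives a range only.
- **That Protocol 12.5 needs the same change.** It names no geometric mean, so it contains no conflict.

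**Conclusion.** Wrong as written. Followed exactly, SAP section 6 gives a zero or undefined geometric mean at any sampling time with at least one concentration below the limit. That result is certain arithmetic and needs no assumption.

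How often it matters does rest on assumptions. With 1% to 5% of samples below the limit, 35 subjects per sampling time and independence between subjects, the chance of losing the statistic at a given time after first dosing is about 30% to 83%.

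The reach is small: one descriptive statistic, for two analytes, in the by-timepoint concentration tables. The overall response rate, the sample size and the population PK modelling are untouched. This is a minor correction worth making because it costs almost nothing.

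**What to change.** In SAP section 6, keep zero for the arithmetic mean, standard deviation, median, minimum and maximum. Then add, for example: the geometric mean is calculated from quantifiable concentrations only; the number of quantifiable values and the number below the limit are shown beside it; it is not reported when half or more of the values at that sampling time are below the limit.

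Under this rule the first predose sample would show no geometric mean, as it should.

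The cost is a sentence or two in the SAP and two counts in the table shell. There is one small downside: the geometric mean uses fewer subjects than the other statistics in its row and is biased slightly upward, because the values left out are the lowest. The displayed counts make this visible. Substituting a fraction of the assay limit would avoid dropping subjects, but the result then depends on a limit that the documents do not give. In the 35-value example, half of an assumed limit of 0.5 gives 10 × (0.25/10)^(1/35) = 9.0, and half of an assumed limit of 2 gives 10 × (1/10)^(1/35) = 9.4.

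No change to Protocol 12.5 is needed. If the tables have already been produced, a footnote stating the rule actually used would serve the same purpose.
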